Frequency of flushing depends on the use of the implanted port catheter (ie. frequency of visits in the out-patient/in-patient units for blood draws or intravenous treatments). At TriHealth, implanted port catheters that are not in use are flushed a minimum of every three months with the same solutions and volumes as noted above (i.e., 20 mL normal saline plus 5 mL heparin (100 units/mL)). The policy also recommends turbulent flushing (see Appendix A). The turbulent flushing technique is accomplished by a push-pause rhythm every one mL for the entire flush volume. Turbulent flushing helps remove built-up residue, medication, and fibrin from the walls of the catheter. There is no policy stating frequency of maintenance port flushes at UCMC Barret Infusion Center. Additionally, TriHealth and UCMC have adopted the use of a neutral displacement needle-free connector with a clear housing (the MicroCLAVE® Clear, ICU Medical, Inc., San Clemente, CA, USA) that features a split septum with a straight internal fluid path design and minimal dead space to help minimize blood reflux into the tip of the catheter upon connection and disconnection of the luerloc, thus reducing the risk of occlusions due to blood reflux. This connector meets recommendations of the Infusion Nursing Society, Center for Disease Control, Federal Drug Administration and Society for Healthcare Epidemiology in America regarding the prevention of intravascular catheter-related bloodstream infections and enables clinicians to view the fluid pathway to verify effective flushing and clamp the IV line without requiring a specific clamping sequence.

State of the Evidence: Heparin plus Saline versus Saline Only for Flushing Central Venous Access Devices.

The most common reason for placing a long term central venous access device (CVAD) in the cancer patient is to deliver chemotherapy. For the cancer patient receiving vesicant drugs, a CVAD is very common for treatment.

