Setting for the Study: TCI Infusion Centers, specifically: the TCI Good Samaritan (GS) Infusion Center at GSH; the TCI GS Infusion Center Butler County; the the TCI GS Infusion Center at the Thomas Center; the TCI GS Infusion Center, Cheviot; the TCI GS Infusion Center, Medicenter; the TCI GS Infusion Center, Anderson; and the McCullough Hyde

Memorial Hospital infusion center. In January 2018, University of Cincinnati Medical Center Barrett Infusion Center was added as a data collection site.

Participants: Patients receiving care in the identified settings who have an implanted port catheter will be recruited to participate in this study.

Inclusion Criteria:

- over the age of 18 years
- able to read and understand English
- has an implanted port in place less than one (1) year
- evidence of a patent port catheter prior to enrollment in the study
- is receiving active treatment i.e., receiving a therapeutic drug through the implanted port
- current treatment protocol projected to continue for a minimum of three (3) months
- anticipates receiving care at the identified centers for 6 months following enrollment in the study
- receives routine care of the implanted port catheter at any of the identified data collection sites

Exclusion Criteria:

- has documented Heparin platelet antibody (could not be randomized to either group) or other allergy to Heparin
- receiving therapeutic dose of an anticoagulant, i.e., warfarin, heparin, enoxaparin, etc.
- has a heparin-coated port (for example BioFlo port)
- does not meet one or more of the inclusion criteria

Recruitment

Prospective study participants will be identified the day prior to their appointment in the treatment center by a member of the research team. Their chart will be reviewed for inclusion criteria and flagged as a potential study participant.

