Based on the literature and our own experience we estimated an approximate occlusion rate of 20% with the standard treatment (saline + heparinized saline flush as described above). The power analysis conducted by [name] determined that, using a two-group normal approximation test of proportions with a one-sided .05 significance level, a sample size of 198 participants per group will have 80% power to reject the null hypothesis that the proposed method is not inferior (i.e. the difference in proportions between the proposed method and the standard method is greater than 0.10). Thus, we will continue data collection until 198 have been completed in each group for a total of 396 study participants who completed 6 months of data collection. To date (July 3, 2019), 69.7% of patients enrolled in the study are able to complete 6 months of data collection without withdrawing for an exclusion criterion (ex: transferring to hospice, being started on an anticoagulant, etc). Therefore, we plan to consent 575 patients to result in 396 who complete the study. Once 396 patients have completed 6 months of data collection will stop and any remaining active participants will be withdrawn from the study.

Data Collection:

Independent Variables: Method for flushing implanted port catheters:

• 20 mL of saline followed by 5 mL of Heparinized saline in a concentration of 100 units/mL

OR

• 20 mL of saline only

Dependent Variables:

Primary Outcomes

- Occurrence of first complete (can neither withdraw blood nor flush the catheter) occlusion
- Occurrence of first partial (able to flush but unable to withdraw blood) occlusion
- Frequency with which alteplase (CathFlo) has to be utilized to resolve an occlusion

Secondary Outcomes

- Number of subsequent occurrences of complete or partial occlusions after the first occurrence.
- Amount of time in days that a port remains patent (flushes easily and able to obtain a blood return).
 - Amount of time between entrance in study and first incidence of partial or complete occlusion
 - Amount of time between incidences of partial or complete occlusion.
- Occurrence of other complications:
 - Central Line-Associated Blood Stream Infection (CLABSI) a laboratory-confirmed (recognized pathogen cultured from one or more blood cultures; organism cultured from blood is not related to an infection at another site) blood stream infection that is considered central line associated (CDC, 2012).
 - Develops complication related to Heparin

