With each visit to the identified treatment center, the nurse will document the date and characteristics related to the patency of the port catheter on the Record of Flushes data collection tool. In the event the blood withdrawal is sluggish or absent, the patient will receive a dose of alteplase (CathFlo) according to the data collection site's policy as ordered by the physician. Dosage and results of that intervention will also be recorded on the Record of Flushes data collection tool. In the event that any study participant (regardless of group assignment) requires alteplase (CathFlo) on three (3) consecutive visits to the treatment center, the patient's participation in the study will be terminated and they will be excluded from further data collection. The patient will be returned to a standard maintenance protocol for flushing of the port as prescribed by the afore-mentioned site policy or as prescribed by attending physician.

Participants in the control group will have yellow colored data collection Face Sheets while participants in the intervention group will have blue colored data collection Face Sheets. The Record of Flushes sheet will be white for patients in both groups. A blue or yellow sticker will be placed on the cover of the patient folder housed in treatment center noting the patient's involvement in the study. The data collection Face Sheet and the current Record of Flushes sheet will be kept in the individual patient folder as long as they remain a participant in the study. As the Record of Flushes data sheet becomes full, they will be collected by study staff and placed in locked drawer in a TriHealth or UCMC Barrett Infusion center office.

In January 2018, UCMC Barrett Infusion Center was added as a new site. The study nurses at UCMC Barrett Infusion Center will use the same data collection forms and will store them along with completed informed consent forms at a locked office at UCMC Barrett Infusion Center. Periodically, the lead research coordinator will bring de-identified data collection forms back to TriHealth. Signed informed consent forms will remain locked on UCMC Barrett Infusion Center property.

Experimental Aspect of the Study:

Patients who agree to participate in this study will be randomized to either the control group or intervention group as explained above.

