Participants in the control group will have their implanted port catheters flushed according to the established site's policy. Following the use of the port catheter with no continuous fluids running, or before de-accessing a port catheter (removing the port needle), the port will be flushed with 20 ml of normal saline and 5 ml of heparinized saline in the concentration of 100 units of heparin per ml.

Participants in the intervention group will have their ports flushed with normal saline only. That is, following the use of the port catheter with no continuous fluids running, or before de-accessing a port catheter (removing the port needle), the port will be flushed with 20 ml of normal saline. Turbulent flushing technique (the solution is injected using a push/pause technique every 1 mL) will be used in both groups and all accessed port catheters will have a neutral displacement connector. The MicroCLAVE[®] Clear displacement connector (ICU Medical, Inc., San Clemente, CA, USA) is the current product in use. Participants in both groups will be seen in a TriHealth Cancer Institute Infusion Center or the UCMC Barrett Infusion Center at a frequency consistent with their individual treatment plan and as outlined in the site's policy. Participants will remain in the study for 6 months or until they experience one of the potential risks noted below. Participants will be considered as having completed the study if they participate for 6 months.

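### The secondary time outcomes can be dated only to the access at which an occlusion is found, so days patent will be overstated; the plan gives no dating rule and no time-to-event method

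*Combined protocol and SAP*

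**What the plan says.** Under Dependent Variables, Secondary Outcomes, the protocol lists the number of days a port remains patent, with two components: "Amount of time between entrance in study and first incidence of partial or complete occlusion" and "Amount of time between incidences of partial or complete occlusion". Partial and complete occlusion are both defined by an attempt to flush and to withdraw blood, so neither can be seen between accesses.

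The Data collection tool section states when patency is recorded: "With each visit to the identified treatment center, the nurse will document the date and characteristics related to the patency of the port catheter". Under Experimental Aspect of the Study, participants are seen "at a frequency consistent with their individual treatment plan and as outlined in the site's policy", and follow-up is six months. The Inclusion Criteria ask for a "current treatment protocol projected to continue for a minimum of three (3) months". The background section on frequency of flushing adds: "At TriHealth, implanted port catheters that are not in use are flushed a minimum of every three months". The same section says that the second institution has no policy on how often maintenance flushes occur.

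The Statistical Analysis section names the t-test, chi-square and Fisher's exact test for the dependent variables, and regression for the effect of the moderating variables on occurrence of occlusion. It also stratifies by flushing frequency, for the rate of occlusion. It names no time-to-event method and gives no rule for dating an occlusion.

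**The concern.** A time in days implies that the day of occlusion is known. Here the record gives only a window that closes on the visit date. If that date is used as the onset, every time to occlusion is too long, by an amount set by the gap between accesses.

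The gap can change within a participant. Treatment need be projected for only three months of a six-month follow-up, and an unused TriHealth port may then go three months between flushes. One permitted gap can therefore cover half of follow-up. A reader would take the reported days patent as a property of the flush solution, when part of the figure comes from the visit calendar.

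The named method adds a second problem. Ports that never occlude have no time to first occlusion, so a t-test on that variable can use only the ports that do occlude.

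**Working it through.** **The plan's own figure.** The sample size concerns proportions. With 20% in both arms, margin 0.10, one-sided 0.05 and 80% power:

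n = (1.645 + 0.842)² × 2 × 0.20 × 0.80 / 0.10² = 197.8, so 198 per group, as stated. No time in days enters it.

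**Inputs for the time outcomes.** From the protocol: 20% occlusion on standard treatment, six months of follow-up (taken as 180 days), the three-month minimum for projected treatment, and three-monthly flushing of unused TriHealth ports. Assumed, because the protocol gives no figure: a constant hazard, and treatment visits every 7, 14 or 21 days.

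**Hazard.** λ = −ln(0.80)/180 = 0.00124 per day.

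**Mean delay for an onset within a gap of w days.** w − [1/λ − w·e^(−λw)/(1 − e^(−λw))], which is close to w/2 + λw²/12.

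| Gap w (days) | Mean delay (days) |
|---|---|
| 7 | 3.5 |
| 14 | 7.0 |
| 21 | 10.5 |
| 90 | 45 + 0.84 = 45.8 |

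**Regular visits.** With accesses every 21 days to day 168 and a last one at day 180, 94% of detected onsets fall in 21-day gaps and 6% in the final 12-day gap, where the mean delay is 6.0 days. The mean delay is 0.94 × 10.55 + 0.06 × 6.0 = 10.3 days (recorded mean 96.9, true mean 86.7).

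**Upper-end case.** Accesses at days 21, 42, 63 and 84, then day 174.

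- Onset by day 84: 1 − e^(−84λ) = 0.0989. Onset by day 174: 0.1940.
- Share of detected occlusions with onset after day 84: (0.1940 − 0.0989)/0.1940 = 49%.
- Mean delay: 0.51 × 10.55 + 0.49 × 45.84 = 27.8 days (recorded mean 111.7, true mean 83.9).
- With 14-day treatment visits before the same 90-day gap, the mean delay is 26.1 days, so the treatment cycle matters little.

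**Effect on the binary outcome.** In the upper-end case 19.4% of ports are found occluded by day 174, against 20.0% truly occluded by day 180. The shortfall is 0.6 percentage points.

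**Effect on the comparison between arms.** Simulation of the upper-end schedule with 198 per arm, constant hazards, 20% against 30% occlusion and two-sided 5% tests:

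| Method | Power |
|---|---|
| t-test on detection days, occluded ports only | about 4 to 5% |
| Log-rank test on detection dates, all ports | about 61 to 62% |
| Interval-censored exponential model, all ports | about 61 to 63% |

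With no true difference, the log-rank test and the interval-censored model both reject in about 5% of runs. The large step is from the t-test to a time-to-event method. Interval censoring adds almost nothing to power.

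**The case against.** **The upper-end case is not the expected one.** It places every participant at two floors at once: the shortest projected treatment and the lowest TriHealth flushing frequency. The protocol does not say how many participants would be there. This stands, and the 28-day figure should be read only as a scenario. Regular treatment visits of 7 to 21 days give an error of about 3.5 to 10.5 days. Three months is not a ceiling at the second institution, where no maintenance interval is set.

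**Randomisation balances the error.** Visits follow the treatment plan and site policy, not the arm, so lateness should be similar in both groups. This stands. A reader might infer that the sparse period hides a difference between arms and pulls the comparison towards equality. The evidence does not support that: a higher hazard in one arm still appears as more ports found occluded at the next access, and the log-rank test on detection dates loses almost nothing against the interval-censored model. Balance does not, however, correct the reported days.

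**The plan does not say that the detection date is the occlusion date.** This is correct. A reader might infer such a rule, but the plan is silent on dating, and the silence is the criticism.

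**Flushing frequency is already considered.** It is a moderating variable for occurrence of occlusion and a stratifier for its rate. Neither use corrects a date.

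**Only secondary outcomes are involved.** This stands. The primary comparison, the margin and the interim looks rest on proportions.

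**Conclusion.** The point holds for the secondary time outcomes. As planned, days patent and time to first occlusion would be late by about half an access gap: about 10 days with 21-day visits throughout, and about 28 days on average in the upper-end case (about 46 days for onsets after treatment ends). These sizes assume a constant hazard, 20% occlusion by six months, and visit schedules that the protocol does not give.

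The title of these outcomes might tempt a reader to conclude that they record only the calendar. That goes too far: while treatment visits are frequent, the error is at most one visit gap, and it dominates only after access becomes sparse. The dating error mainly harms the day values. The weakness in the comparison between arms comes from the t-test, not from the gaps. The 198 per group is unaffected, and the binary primary comparison essentially so. The change should be made, but it does not threaten the trial's main conclusion.

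**What to change.** In the Statistical Analysis section:

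1. Replace the t-test on days by an interval-censored analysis of time to first occlusion in all randomised participants, for example a Weibull or proportional hazards model with arm as covariate. Bound each onset by the last access at which the port was patent and the first at which it was not. Censor ports that never occlude at their last patent access.
2. Report the distribution of access intervals by arm, separately on and after treatment.
3. Label any summary based on detection dates, including times between occlusions, as time to detection and not as days patent.

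The Record of Flushes already holds the date and patency at each visit, so no new data are needed and no clinical procedure changes. The cost is a change of wording, a standard model, slightly wider intervals and a less familiar summary. The gain in power between arms comes from using a time-to-event method at all; interval censoring mainly corrects the day estimates.

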Heparin induced thrombocytopenia (HIT) is an immune reaction to heparin. Through a series of steps, antibodies are produced in response to an immune complex, which in turn activates platelets. As activated platelets are destroyed, thrombocytopenia (low platelet count) occurs. This ultimately leads to a thrombotic state. Patients experiencing HIT can develop deep venous thrombosis, pulmonary emboli, stroke, or myocardial infarction. Patients developing HIT thrombotic syndrome may require limb amputation and are at increased risk for death. The actual incidence of HIT is 1-5% of patients exposed to heparin (Cooney, 2006). Many clinicians think that HIT is under-recognized and under diagnosed. The first response to the diagnosis of HIT is the discontinuation of all forms of heparin, including heparin flushes. The use of heparin should be avoided or minimized whenever possible. If saline only flushes were found to be as effective as heparinized saline flushes, it would significantly decrease the patient's exposure to heparin, and therefore the potential to develop HIT.

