 - HIT (Heparin induced thrombocytopenia as measured by a positive HIT antibody test)
 - Other heparin allergy

Moderating variables: other things that could also affect patency of the port

- Number of times port flushed per month or frequency of flushing.
- Use of prophylactic doses of anticoagulant drugs (e.g., enoxaparin, heparin, warfarin)
- Development of a hypercoaguable state, as diagnosed by primary hematologist/oncologist
- Mechanical difficulties related to port placement e.g. "Pinch-off syndrome"
- Length of time port has been in place prior to entrance in study

Extraneous variables:

- Type of cancer
- Age of participant

Data collection tool

The data collection tool (see Implanted Port Catheter Flushing Data Collection Form – Face Sheet: Appendix C and Record of Flushes: Appendix D) were developed by the principal and sub-investigators specifically for the purpose of this study. The tool was reviewed by the OPCC nurses for completeness and clarity. In addition to basic demographic information (age, gender), the nurse will record the patient's type of cancer, and the diagnosis or history of any hypercoaguable state or use of anticoagulant medication as documented in the patient chart. The nurse will also document the type of implanted port catheter (single/double), the port location (right/left, subclavian vein (described in the operative note or chest x-ray), and the date the port was inserted so that length of time the port has been in place can be calculated. Data will be recorded on the Face Sheet when the patient is enrolled in the study and as pertinent information/events become known, i.e., as complications occur.

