Potential risks for study participants in either arm of the study include partial occlusion (can instill flush solution but not withdraw blood) and complete occlusion (can neither instill flush solution nor withdraw blood). Study participants could require removal of the port if an occlusion cannot be resolved, and possibly require re-insertion of a new implanted port. In the event of any occlusion, alteplase (CathFlo) in the policy established dose and frequency (see Appendix A) will be instilled to resolve the occlusion. Study participants whose implanted ports are found occluded on three (3) consecutive visits to the treatment center will be excluded from further data collection, i.e., their participation in the study will be terminated. The standard flushing as prescribed by the site's policy or as prescribed by the attending physician will be used. Study participants whose occlusion cannot be resolved with alteplase and require removal of the port will also be terminated and excluded from further data collection. Patients who develop port infections necessitating port removal will be terminated and excluded from further data collection. Study participants who develop HIT (heparin induced thrombocytopenia) or other heparin allergy will be terminated and excluded from further data collection. Likewise, patients who have thrombotic or embolic phenomenon requiring therapeutic anticoagulation will be terminated and excluded from further data collection. If a participant in the intervention group receives clinical care and their port is flushed with heparin (following standard hospital policy), the participant will be withdrawn from the study.

The study will be closed if there is evidence that study participants in the intervention arm experience implanted port occlusion at a disproportionate rate. The amount of alteplase (CathFlo) used in each group will be assessed each

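### The HIT outcome is met by a positive antibody test alone, although the protocol describes thrombocytopenia as a later step, so antibody-only results would count as HIT

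*Combined protocol and SAP*

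**What the plan says.** Under Dependent Variables, Secondary Outcomes, complications related to heparin include "HIT (Heparin induced thrombocytopenia as measured by a positive HIT antibody test". Nothing else in the available text adds a platelet count, a confirmatory assay, a clinical score or adjudication.

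The Background section (care of implanted ports at TriHealth) describes a chain of events: "antibodies are produced in response to an immune complex, which in turn activates platelets", and then "As activated platelets are destroyed, thrombocytopenia (low platelet count) occurs". It also states: "The actual incidence of HIT is 1-5% of patients exposed to heparin" and "Many clinicians think that HIT is under-recognized and under diagnosed".

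Three other places bear on how the outcome works:

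- **Exclusion Criteria.** A patient is excluded who "has documented Heparin platelet antibody (could not be randomized to either group) or other allergy to Heparin". Only a documented antibody counts, and no baseline test is described.
- **Inclusion Criteria.** A participant "has an implanted port in place less than one (1) year". The site policy described in the Background section is a heparinized final flush, so exposure before enrollment is possible in both arms.
- **Experimental Aspect of the Study.** "Study participants who develop HIT (heparin induced thrombocytopenia) or other heparin allergy will be terminated and excluded from further data collection".

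HIT is among the complications named in the purpose statement and falls under research question 2. The Statistical Analysis section compares the dependent variables between groups by t-test, chi-square or Fisher's exact test.

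**The concern.** The outcome is named after the last step in the protocol's chain but measured at the first. A positive antibody test with an unchanged platelet count satisfies it. A count of antibody results could then be reported as a disease rate.

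A positive test also cannot by itself place the onset after randomisation. Participants may have received heparin flushes for up to a year before entry, and those never tested are not excluded. A positive result already present at entry, in either arm, could be recorded as a study event.

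Avoiding HIT is the main safety argument the protocol gives for dropping heparin, so this item will carry weight in any conclusion about which flush is safer. It is also a sparse outcome, where a handful of misclassified results matters.

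The HIT termination rule uses the same term without its own definition. If the outcome definition is carried over to it, an antibody-only result ends data collection for that participant.

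**Working it through.** **1. The plan's own figure.** The Recruitment section gives 198 per group (occlusion rate 20%, margin 0.10, one-sided alpha 0.05, power 80%):

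n = (1.645 + 0.842)² × 2 × 0.20 × 0.80 / 0.10² = 6.183 × 32 ≈ 198.

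This reproduces. No HIT quantity enters it, so the primary sample size and alpha do not depend on this point.

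**2. Expected HIT cases in the heparin arm**, using the Background incidence of 1-5%:

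- 198 × 0.01 = 1.98
- 198 × 0.05 = 9.9

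The figure of 198 counts completers. If all 575 planned consents were split evenly (287.5 per arm), the range would be 2.9 to 14.4. The outcome is sparse on either base.

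**3. Antibody-only results that could be added.** Let h be the true HIT rate, a the antibody-only rate among those tested, and t the share tested. The documents give neither a nor t. The assumed ranges are a = 1-10% and t = 5-100%.

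Extra cases = 198 × (1 − h) × a × t; ratio of counted to true = 1 + extra / (198 × h).

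| h | a | t | True | Extra | Counted/true |
|---|---|---|---|---|---|
| 1% | 1% | 5% | 2.0 | 0.1 | 1.05 |
| 1% | 10% | 20% | 2.0 | 3.9 | 2.98 |
| 1% | 10% | 100% | 2.0 | 19.6 | 10.9 |
| 5% | 1% | 5% | 9.9 | 0.1 | 1.01 |
| 5% | 10% | 20% | 9.9 | 3.8 | 1.38 |
| 5% | 10% | 100% | 9.9 | 18.8 | 2.9 |

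The addition runs from about 0.1 to 20 cases, depending wholly on inputs that the documents do not supply.

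**4. Direction.** Suppose antibody-only results occur at the same rate a in both arms with everyone tested, and true HIT occurs only in the heparin arm. The observed risk difference is then h + (1 − h)a − a = h(1 − a). With h = 1%, it is 0.99 points at a = 1%, 0.95 at 5% and 0.90 at 10%, against a true 1.0. The difference shrinks slightly; it does not grow. It grows only if antibody-only results, or testing, are more frequent in the heparin arm.

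**5. How few results matter.** Two-sided Fisher's exact test, 198 per arm, illustrative counts (heparin versus saline):

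- 2 versus 0: p = 0.50
- four antibody-only results added to the heparin arm, 6 versus 0: p = 0.030
- four added to each arm, 6 versus 4: p = 0.75

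The same definition can create a nominally significant difference or leave none, according to where the antibody-only results fall. With no HIT in the saline arm and no misclassification, power at the two-sided 0.05 level is about 1.5% if the heparin-arm rate is 1%, and 93% if it is 5%.

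**The case against.** The strongest reply is that the definition is being read at its worst. The item sits under heparin-related complications and names thrombocytopenia, so it could mean thrombocytopenia supported by a positive test. No antibody screening is described, and complications are recorded as they become known. If tests are ordered only on clinical suspicion, antibody-only results may be few. The Background section gives a sequence and does not say how often antibodies occur without a platelet fall. These points limit the size of the problem. They do not remove it: the written criterion is the antibody test, and nothing in the available text says that testing follows suspicion.

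A reader might infer that the definition overstates heparin harm, perhaps two- to three-fold. The documents do not support that. Such a multiple is simply 1 + k, where k is an assumed number of antibody-only results per true case. Uneven testing is conceivable, because only one arm is assigned heparin and staff can see the group sticker. But heparin exposure before enrollment could put positives in both arms and dilute the difference, and the protocol itself says that HIT is thought to be under-diagnosed.

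The base of 2 to 10 cases may also be high. The quoted 1-5% refers to heparin exposure generally. The Background section reports one patient with documented HIT in the outpatient center over about a year, against 391 port patients in FY 2012. Scaled crudely, 198 × 1/391 ≈ 0.5 case. The periods may not match and this is not an incidence rate, but it is a fair caution. An even smaller base makes each misclassified result matter more.

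A reader might also infer material damage to the occlusion comparison through terminations. That is not shown. The termination rule does not say that antibody positivity alone triggers it, recruitment continues until 198 per group complete, and about 30% non-completion is already planned for.

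**Conclusion.** The concern holds as a mismatch between the outcome's name and its measurement. By the protocol's own account thrombocytopenia follows antibody formation, yet an antibody result alone is enough to count as HIT. This is a stated rule, not an omitted detail, and it can misclassify results in a secondary safety comparison.

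About 2 to 10 heparin-arm cases would be expected, if the protocol's 1-5% applies to port flushes and cases are detected. Against that base a few antibody-only results could change the comparison materially. Neither the direction nor the size of any bias can be established; the range of 0.1 to 20 extra cases rests entirely on assumed positivity and testing rates. The finding is confined to this secondary outcome and to the clarity of the termination wording.

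**What to change.** - Count HIT as a positive antibody test together with a documented fall in platelet count after randomisation, taken from the chart.
- Report antibody-positive results without a platelet fall as a separate outcome.
- Report the number of participants tested in each arm, so that uneven ascertainment can be seen.
- Reconcile the Background description, the exclusion criterion, the outcome definition and the HIT termination wording on what developing HIT means for ending participation. The exclusion criterion already treats a documented antibody as disqualifying, so the sections may intend different things. Which finding should end participation is left to the investigators.

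The cost is a change of wording and an added data item. No new test is needed if platelet counts are available in the chart, which is an assumption: the data-collection description does not mention them, and the face sheet is not in the available text. Fewer HIT events will be counted, and a platelet fall during chemotherapy is not specific to HIT. For that second reason the antibody-only results should be reported alongside. Making the treating clinician's attribution the main criterion would not be an improvement, since that clinician can know the assigned flush.
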